8.3.2. Relationship of AEs to the Investigational Medicinal Product

The Investigator will assess the causal relationship between the AE and the IMP (either ladarixin or placebo), according to the criteria in the **Table** below:

Relationship of the AEs to the IMP

None (Intercurrent Event)	An event that is not and cannot be related to the Investigational Product, e.g. a surgical intervention for nevus removal performed during the study, but planned before patient enrolment into the study
Unlikely (remote)	Relationship is not likely e.g. a clinical event including laboratory test abnormality with temporal relationship to drug administration which makes a causal relationship improbable and in which other drugs, chemicals or underlying disease provide more plausible explanations
Possible	Relationship may exist, but could have been produced by the patient's condition or treatment or other cause
Probable	Relationship is likely, the AE abates upon discontinuation of Investigational Product and cannot be due to the patient's condition
Highly Probable	Strong relationship, the event abates upon discontinuation of Investigational Product and, if applicable, re-appears upon repeat exposure

Any AE reported in the study having a possible, probable or highly probable relationship to the study drug will be considered as an ADR.

8.3.3. Severity of adverse events

The Investigator will grade the severity of any AE using the definitions in the **Table** below. For each episode, the highest severity grade attained should be reported.

Severity of the Adverse Event

Mild	Grade 1 - Does not interfere with patient's usual function (awareness of symptoms or signs, but easily tolerated [acceptable]).
Moderate	Grade 2 - Interferes to some extent with patient's usual function (enough discomfort to interfere with usual activity [disturbing]).
Severe	Grade 3 - Interferes significantly with patient's usual function (incapacity to work or to do usual activities [unacceptable])

8.4. SERIOUS ADVERSE EVENT REPORTING

8.4.1. Reporting Procedure for the Investigator to Dompé/CRO

The Principal Investigator must report all SAEs occurring during patient participation in the study, regardless of presumed causal relationship, to the appropriate Sponsor/CRO Pharmacovigilance contact by e-mail (preferred) or fax **within 24 hours** of learning of the event. Contact details for SAE reporting by the Investigator are provided in the section “Contact Information” (See Page 2 of this Protocol).

The Investigator should also report information on SAEs that continue after patient has completed his/her participation in the study (whether study completion or withdrawal), unless patient has withdrawn his/her consent.

In line with CT3 Detailed Guidance and ICH E2A provisions, although the Investigator does not usually need to actively monitor patients for AEs once the trial has ended, if the Investigator becomes aware of a SAE occurring to a patient after that patient has ended his/her participation in the study (whether study completion or withdrawal), the SAE should be reported by the Investigator to the appropriate Pharmacovigilance or directly to the Dompé Global Pharmacovigilance, Safety and Surveillance Department, should the whole study have been ended. Such “post-study cases” should be regarded for expedited reporting purposes as though they were study reports. Therefore, a causality assessment and determination of expectedness are needed for a decision on whether or not expedited reporting is required.

Information on SAEs will be recorded on a specific SAE form. Both electronic and blank paper copies will be included in the Investigator’s Site File. Follow-up reports (as many as required) should be completed and e-mailed/faxed following the same procedure above.

Whenever more than one SAE is observed, the Investigator should identify which is the primary adverse event, i.e. the most relevant one. If other events are listed in the same report, the Investigator, along with their relatedness to the Investigational Product, should identify which adverse events are serious and which are non-serious. In any case, the Investigator is requested to record his/her opinion about the relatedness of the observed event(s) with the investigational medication.

8.4.2. Conditions that should not be reported as serious adverse events

The conditions listed below, that may require hospitalization of a patient, are not considered to be SAE and shall not be reported as such, but only need to be recorded in the eCRF:

- Hospitalizations planned before entry into the clinical study which is part of the normal treatment or monitoring of the studied indication and not associated with any deterioration in condition.
- Hospitalization for routine treatment or monitoring of the studied indication, not associated with any deterioration in condition.
- Hospitalization for treatments, which was elective or pre-planned, for a pre-existing condition that is unrelated to the indication under study and did not worsen.
- Treatment on an emergency, outpatient basis for an event not fulfilling any of the definitions of SAEs given above and not resulting in hospital admission.

In addition, the following situation shall not be considered SAE:

- Abnormal laboratory values or test results that do not induce clinical signs and/or symptoms and do not require intervention/therapy, i.e. are clinically significant.

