5.3.2. Criteria for discontinuation of the IMP

The IMP will be discontinued in the case:

- QTcF is either > 500 msec or increases by > 60 msec from screening measurement on two consecutive ECG readings taken 1 hour apart;
- The patient develops any significant cardiovascular disease/abnormality;
- The patient develops renal (calculated eGFR < 60 mL/min) or hepatic (increased ALT/AST > 3 x ULN and increased total bilirubin > 3mg/dL [$>51.3 \mu\text{mol/L}$]) dysfunction as well as hypoalbuminemia (serum albumin <3 g/dL);

- Pregnancy occurs (subjects of child-bearing potential);
- The patient develops Diabetic Ketoacidosis (**DKA**) or hypoglycemic coma.

Occurrence of any condition that qualify the patient to treatment discontinuation will be specifically monitored through ECG readings and safety laboratory tests obtained at week 4 (visit 2b) and 11/12 (visit 3) during treatment. Pregnancy (urine dipstick) will be also tested at week 11/12 (visit 3).

In addition, the IMP will be immediately discontinued in the event of any other possibly drug related occurrences that the study physician believes might compromise patient's safety.

If the IMP administration is prematurely discontinued, the primary reason for discontinuation must be recorded in the eCRF. Patients who discontinue the treatment with the IMP will NOT be withdrawn from the study by default but will be asked to complete safety and efficacy observations as per the protocol, unless otherwise they withdraw their consent.

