- is medically significant or important medical condition, i.e. an important medical event that based upon appropriate medical judgment, may jeopardize the patient and may require medical or surgical intervention to prevent one of the outcomes listed above.

NOTE: An important medical condition is an event that may not result in death, be life-threatening, or require hospitalization but may be considered a SAE when, based upon appropriate medical judgment, it may jeopardize the patient and may require medical or surgical intervention to prevent one of the outcomes listed above. Examples of such medical events include allergic bronchospasm requiring intensive treatment in an emergency room or at home, blood dyscrasias or convulsions that do not result in patient hospitalization, or the development of drug dependency or drug abuse.

Pre-planned hospitalization or hospitalization for routine treatment or monitoring of the studied indication, not associated with any deterioration in condition are not considered to be serious events. These events must be recorded in the AE section (except for hospitalization for study procedures) of the eCRF where a variable will be ticked to indicate that they are not SAEs.

Death shall always be reported as SAE, and cause of death shall always be specified, when known.

Unexpected Adverse Events

An AE or ADR is considered **unexpected** if it is not listed in the Investigator Brochure (Reference Safety Information section). An event is unexpected also when it is not listed at the specificity or severity that has been observed and listed in the Investigator Brochure. Events that are mentioned in the Investigator Brochure as occurring with a class of drugs or as anticipated from the pharmacological properties of the drug but are not specifically mentioned as occurring with the particular drug under investigation are considered unexpected. The determination of expectedness shall be made on the basis of the IB Reference Safety Information (RSI) section.

According to the Investigator Brochure (Reference to Safety Information, section 6.4), for the purpose of this study all ADRs are assumed to be unexpected.

Suspected unexpected serious adverse reaction

A **suspected unexpected serious adverse reaction (SUSAR)** is defined as an adverse reaction that is both unexpected (not consistent with the applicable product information) and also meets the definition of a Serious Adverse Reaction.

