8.4.4. Reporting Procedure to IEC and to Regulatory Authorities in the European Union

Reporting of Suspected Unexpected Serious Adverse Reaction

Investigator must report all serious adverse events to the sponsor immediately, within 24 hours.

Dompé Global Pharmacovigilance, Safety and Surveillance Department, with the support of the CRO as appropriate, shall report any SUSAR to the concerned IEC which approved the protocol and the Regulatory Authority (via the Eudravigilance Clinical Trial module) as soon as possible, and in no event later than:

- seven calendar days after becoming aware of the information if the event is fatal or life threatening; to be followed by any relevant information within eight days.
- fifteen calendar days after becoming aware of the information if the event is neither fatal nor life threatening.

Treatment will be unblinded by Dompé Global Pharmacovigilance, Safety and Surveillance department prior to regulatory submission of a potential SUSAR to Regulatory Authorities and IEC in the European Union. If the patient is on the active treatment, then Dompé Global Pharmacovigilance, Safety and Surveillance Department will report the case as a SUSAR. If the patient is revealed to have taken a placebo, then this would not require reporting as a SUSAR, unless there are concerns that there is a reaction to something in the placebo (such as an allergic reaction or a contaminant caused by a manufacturing issue).

If the results of an investigation show that an AE not initially determined to be reportable is reclassified as reportable, Dompé shall notify such SUSAR in a written safety report as soon as possible, but in no event later than 7/15 calendar days after the determination is made.

Copies of all correspondence relating to reporting of any SAEs to the IEC should be maintained in the Investigator's Files.

Periodical Reporting to EU Regulatory Authorities

Dompé Global Pharmacovigilance, Safety and Surveillance Department will prepare and submit (via the CRO as applicable) to Investigators appropriate periodical safety updates as per applicable EU and local requirements and regulations. Dompé Global Pharmacovigilance, Safety and Surveillance Department shall also be responsible to prepare and submit annual safety reports (Development Safety Update Report – DSUR) to relevant Regulatory Authorities and to IECs.

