12.5. DATA MONITORING COMMITTEE

An independent DMC will be established and will be responsible for safeguarding the interests of trial participants, and for enhancing the integrity and credibility of the trial. The DMC will assess the safety of the interventions during the trial and will monitor the overall conduct of the clinical trial. The DMC will provide recommendations to Dompé about stopping or continuing the trial on safety basis.

The DMC will operate independently of Dompé, and its members will not have connections to Dompé with the exception of the compensation to DMC members related to their activities.

The DMC will comprise three members. They will be a multidisciplinary group that will include:

- Two diabetologists/endocrinologists with extensive experience in the diagnosis and management of patients with T1D, mainly at disease onset;
- A Biostatistician with substantial experience in the DMC process.

The DMC:

- Will review unblinded data. To this purpose, an Independent Statistician will liaise with the CRO statistician and will have access to those components of the database necessary to generate the reports to the DMC.
- Will be responsible for the ongoing (at least every 4 months) review of safety data throughout the trial. Primary among the safety data that will be reviewed are Serious AEs.
- Will have also access to unblinded information on the primary analyses to enable the assessment of the acceptability of safety in the context of emerging evidence about efficacy.
- Will be advisory to Dompé and make recommendations to Dompé regarding the continuation of the trial and potential modifications to the design and conduct of the trial. These recommendations will be made in a manner to maintain confidentiality of emerging information about efficacy and safety, unless access to certain data is needed to enable Dompé to make decisions about the DMC recommendations. Dompé will be responsible for promptly reviewing the DMC recommendations, to decide whether to continue or terminate the trial, and to determine whether amendments to the protocol or changes in the study conduct are required

All details of the conduct and responsibilities of the DMC will comply with [Guidance for Clinical Trial Sponsors: Establishment and Operation of Clinical Trial Data Monitoring Committees](#) and will be described in the 'DMC Charter' to be finalized during the set-up phase of the study and prior to the initiation of treatment.

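### Section 8.4.2 describes the abnormal results it excludes from SAE status as clinically significant, which contradicts its own two conditions and the important-medical-event criterion in 8.1

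*Protocol*

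**What the plan says.** Section 8.4.2 first lists hospitalizations and outpatient emergency treatment that need not be reported as serious. It then adds a mandatory exclusion, introduced by "In addition, the following situation shall not be considered SAE". The situation is: "Abnormal laboratory values or test results that do not induce clinical signs and/or symptoms and do not require intervention/therapy, i.e. are clinically significant".

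Three other parts of the protocol bear on it:

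- **Section 8.1** allows an event to be serious, even without hospitalization, when it is "an important medical event that based upon appropriate medical judgment, may jeopardize the patient" and may require intervention to prevent one of the listed serious outcomes.
- **Sections 8.4.1, 8.4.4 and 8.4.5** attach the fast reporting duty to seriousness. In 8.4.4: "Investigator must report all serious adverse events to the sponsor immediately, within 24 hours".
- **Section 5.3.2** discontinues the IMP on several criteria, four of which are pure test values. One is "QTcF is either > 500 msec or increases by > 60 msec from screening measurement on two consecutive ECG readings taken 1 hour apart". The others are an eGFR limit, raised ALT/AST together with raised bilirubin, and low serum albumin. When the IMP is stopped, "the primary reason for discontinuation must be recorded in the eCRF".

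**The concern.** The sentence in 8.4.2 defines a class of results by two conditions and then restates that class as its opposite. It is an operative rule that investigators apply when deciding whether something goes to the sponsor within 24 hours.

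Seriousness matters more than usual in this trial. Section 8.1 treats every adverse drug reaction as unexpected, so for an event judged drug-related, seriousness is the only remaining step towards SUSAR reporting. The sentence that helps decide seriousness for laboratory and ECG findings is the one that contradicts itself. Laboratory and ECG monitoring is also what section 2.6.2.1 relies on to limit risk, and section 2.5.3 names QT prolongation as a potential concern.

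At stake is consistent classification. Two sites could class the same finding differently, and each could cite the protocol.

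**Working it through.** No arithmetic applies, and the protocol gives no figure to reproduce. The check sets the passages side by side.

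**Step 1: the sentence against itself.** The exclusion needs both conditions: (a) no signs or symptoms, and (b) no intervention or therapy required. The phrase after *i.e.* should restate (a) and (b). A result meeting both would ordinarily be called not clinically significant; the text says it is clinically significant. Section 9.4.2.3 shows that the term is a working category here, because it tabulates abnormal results separately from abnormal clinically significant ones. A literal reader can therefore match the 8.4.2 wording to an actual data category, and it is the wrong one.

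**Step 2: the sentence against 8.1, as printed.** 8.4.2 is mandatory and, on its literal gloss, removes clinically significant results. 8.1 is permissive and lets medical judgment make a finding serious. The two conflict directly for a clinically significant result that an investigator believes may jeopardize the patient.

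**Step 3: the sentence against 8.1, with *not* restored.** Most of the conflict goes. 8.1 covers events that may require intervention, and 8.4.2 excludes results that do not require it. The sets are nearly complementary. What remains is the space between *may require* and *does not require*: a result that is silent and untreated today but that the investigator judges dangerous. The text does not say which section governs.

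**Step 4: the sentence against 5.3.2.** Each of the four value-based criteria (QTcF, eGFR, ALT/AST with bilirubin, albumin) can be met without symptoms. Condition (a) can then hold. Whether (b) holds depends on whether stopping the IMP is intervention or therapy, which the protocol does not define:

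- If stopping counts, the finding falls outside the exclusion and 8.1 decides seriousness.
- If stopping does not count, and nothing else is needed, the exclusion applies and the finding is handled as non-serious.

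**Step 5: what happens to a finding classed as non-serious.** It is not lost. Section 8.1 counts abnormal laboratory findings among possible AEs. Section 8.2 requires clinically relevant changes in protocol parameters to be reported as AEs. Section 8.3 records relationship, severity and action taken. Section 5.3.2 puts the reason for stopping in the eCRF. What such a finding lacks is the 24-hour duty, which covers SAEs only.

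**The case against.** The strongest defence is that this is one dropped word whose intended meaning is plain from the same sentence, and that a trained investigator would read it correctly. The first part is right: the intended sense is hardly in doubt. It does not remove the point, because the sentence is a binding reporting rule and should not depend on readers correcting it.

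The defence is also right to resist several stronger readings that a reader might infer:

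- *That all asymptomatic abnormal results are barred from SAE status.* The exclusion also requires that no treatment be needed.
- *That a result meeting a 5.3.2 criterion ought to be an SAE, so sponsor awareness slips from 24 hours to routine data review.* Meeting a discontinuation criterion is not among the seriousness criteria in 8.1, and the protocol never promised 24 hours for such results. Pregnancy (8.5) and overdose (8.7) have their own 24-hour routes; giving laboratory and ECG criteria one too would be a design preference, not the correction of an error.
- *That such a case can never enter the 7/15-day pathway.* Sections 8.4.4 and 8.4.5 provide for an AE first judged not reportable to be reclassified and then notified within those limits.
- *That the DMC would learn of it late.* Section 12.5 says "Primary among the safety data that will be reviewed are Serious AEs", but the DMC reviews safety data generally, at least every 4 months, and no faster route to it is stated for SAEs either. Report contents belong to the DMC Charter, which is not shown.
- *That the new-onset T1D trial proves the gap.* One of 50 ladarixin patients stopped for ALT/AST increases, and that event is not among the serious events listed in section 2.5.3. No bilirubin, symptoms or treatment are given, so the case shows plausibility only.

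**Conclusion.** The point holds in a limited form. The closing words of 8.4.2 contradict the two conditions they are meant to explain. Read literally, they exclude clinically significant results from SAE status, and hence from 24-hour reporting, in conflict with 8.1. With the missing word restored, a smaller ambiguity remains: the protocol does not say whether the exclusion yields to the important-medical-event judgment, or whether stopping the IMP for one of the four value-based criteria counts as intervention or therapy.

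The size is qualitative. The defect touches safety classification and reporting only and changes no efficacy analysis. How many patients it would affect cannot be derived from the protocol. The conclusion assumes that no other trial document (for example, SAE form instructions or a safety plan) already gives investigators the correct wording. Even if one does, the protocol sentence should be corrected.

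**What to change.** 1. In 8.4.2, insert *not* so that the closing phrase says the excluded results are not clinically significant.
2. In the same place, state that the exclusion does not override the investigator's judgment under 8.1 that a finding is an important medical event.
3. Reconcile 8.4.2 with 5.3.2 by stating whether stopping the IMP for a value-based criterion (QTcF, eGFR, ALT/AST with bilirubin, albumin) counts as intervention or therapy for this rule. The sponsor must decide which; the need is only that every site applies the same answer.

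No threshold, stopping criterion or analysis changes. The cost is a few words in a protocol amendment and a matching line in site training.

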8.4.3. Adverse events exemption

Not applicable.

8.4.4. Reporting Procedure to IEC and to Regulatory Authorities in the European Union

Reporting of Suspected Unexpected Serious Adverse Reaction

Investigator must report all serious adverse events to the sponsor immediately, within 24 hours.

Dompé Global Pharmacovigilance, Safety and Surveillance Department, with the support of the CRO as appropriate, shall report any SUSAR to the concerned IEC which approved the protocol and the Regulatory Authority (via the Eudravigilance Clinical Trial module) as soon as possible, and in no event later than:

- seven calendar days after becoming aware of the information if the event is fatal or life threatening; to be followed by any relevant information within eight days.
- fifteen calendar days after becoming aware of the information if the event is neither fatal nor life threatening.

Treatment will be unblinded by Dompé Global Pharmacovigilance, Safety and Surveillance department prior to regulatory submission of a potential SUSAR to Regulatory Authorities and IEC in the European Union. If the patient is on the active treatment, then Dompé Global Pharmacovigilance, Safety and Surveillance Department will report the case as a SUSAR. If the patient is revealed to have taken a placebo, then this would not require reporting as a SUSAR, unless there are concerns that there is a reaction to something in the placebo (such as an allergic reaction or a contaminant caused by a manufacturing issue).

If the results of an investigation show that an AE not initially determined to be reportable is reclassified as reportable, Dompé shall notify such SUSAR in a written safety report as soon as possible, but in no event later than 7/15 calendar days after the determination is made.

Copies of all correspondence relating to reporting of any SAEs to the IEC should be maintained in the Investigator's Files.

Periodical Reporting to EU Regulatory Authorities

Dompé Global Pharmacovigilance, Safety and Surveillance Department will prepare and submit (via the CRO as applicable) to Investigators appropriate periodical safety updates as per applicable EU and local requirements and regulations. Dompé Global Pharmacovigilance, Safety and Surveillance Department shall also be responsible to prepare and submit annual safety reports (Development Safety Update Report – DSUR) to relevant Regulatory Authorities and to IECs.

